#### 6.5 BASELINE

The baseline used in the analysis for each variable (for which comparison with baseline is requested) is reported in the table below:

Endpoint	Baseline
Laboratory parameters, renal function	Screening
Echocardiographic parameters, VAS	Pre-dose Day 1
score for dyspnoea, vital signs	
BNP, cTnT	Mean (pre-dose 1, pre-dose 2) at Day 1

# 7.0 STATISTICAL METHODOLOGY

## 7.1 HANDLING OF MISSING DATA

The number of patients with missing data will be presented under the "Missing" category, if present. Missing values will be included in the denominator count when computing percentages.

When continuous data are being summarised, only the non-missing values will be evaluated for computing summary statistics.

Missing or incomplete data will be treated as described in sections 6.1, 6.3 and 6.4.

There will be no imputation of missing echocardiographic data.

Other critical missing data will be discussed prior to treatment unblinding, if any. Decisions will be taken during the blind review of the data and will be fully documented in the Data Review Report.

### 7.2 COVARIATES AND SUBGROUPS

Linear Mixed Models for Repeated Measures (MMRM) will include treatment, centre, timepoint, gender, baseline cTnT (normal <URL, abnormal ≥URL), atrial fibrillation (Yes/No) and treatment\*timepoint interaction as fixed effects and baseline and baseline\*timepoint interaction as covariates.

Analysis of Covariance (ANCOVA) models will include treatment, centre, gender, baseline cTnT (normal <URL, abnormal ≥URL) and atrial fibrillation (Yes/No) as fixed effects and baseline as covariate.

ANOVA models for echocardiographic parameters will include treatment only. For analysis of Cohort 1, treatment is defined as (0.5 µg/kg/min dose, placebo). For analysis of Cohort 2, treatment is defined as (1.0 µg/kg/min dose, placebo).

All baseline values considered in the statistical analyses have been defined in the paragraph 6.6.

1.0/30/10/2018 Page 16 of 28

# 7.3 INTERIM ANALYSIS AND SEQUENTIALITY OF ANALYSES

After the completion of cohort I, a safety interim analysis will be performed and the Data Monitoring Committee (DMC) members will evaluate the incidence of cTnT elevation. At interim analysis, the DMC may recommend to do not proceed with the next cohort if the incidence of cTnT elevation is found to be statistically significantly higher on the istaroxime dose than on placebo, or if this difference is deemed to be clinically relevant. Consequently, the clinical study will be prematurely terminated.

Randomization data and datasets needed to conduct the interim analysis will be given by an independent statistician to the DMC statistician. The DMC will be unblinded when performing the interim analysis.

During the interim analysis, DMC members will analyze and discuss the results in closed sessions. The DMC is required to keep confidential and undisclosed until study conclusion: i) these discussions, ii) the detailed minutes thereof, and iii) the interim analysis results.

For the primary endpoint, the primary comparison will be  $0.5 \mu g/kg/min$  dose of istaroxime versus placebo at 24 hours. Highest dose of istaroxime (1.0  $\mu g/kg/min$ ) versus placebo will be tested as a secondary comparison.

# 7.4 GENERAL METHODOLOGY

Descriptive statistics will be provided for all variables in the summary tables by treatment group according to the type of variable summarized.

Quantitative variables will be summarised by using n, mean, standard deviation (SD), 95% confidence interval (CI) of the mean, median and range (minimum and maximum). Categorical variables will be summarised by using frequency distributions and percentages.

Hypothesis testing will be carried out at the alpha = 0.05 level (two-sided) when comparing treatments. For all inferential analyses, p-value will be rounded to three decimal places. Statistical significance will be declared if the rounded p-value will be less than or equal to 0.05.

Statistical analyses will be carried-out pooling together the patients treated with placebo in the two groups with the exception of the echocardiographic parameters that will be analysed separately for each cohort.

All data collected in the CRF will be presented in the listings.

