14.2 Statistic Plan

All statistical analyses will be performed using Statistical Analysis Systems (SAS®) Software

(release 9.2) on a Windows 7 pro operating system.

Sample size

Protocol N°: CVT-CV-002

49

No formal sample size calculation has been calculated since there is no preliminary study to evaluate these endpoints at 24 hours after the infusion start.

In a previous study [14], there was a statistically significant decrease of the primary efficacy endpoint with istaroxime $0.5 \mu g/kg/min$ respect to placebo at 6 hours (twenty-nine patients in both groups). Since this study will investigate the primary efficacy endpoint at 24 hours and it is supposed that the profile at 24 hours should be similar to the one at 6 hours, it is expected that forty patients per group will be sufficient to evaluate a potential difference between istaroxime groups and placebo group on the primary efficacy endpoint at 24 hours.

Descriptive statistics

Descriptive statistics will be provided for each variable in summary tables by treatment group. Quantitative variables will be summarized by using n (sample size), mean, 95% confidence interval (CI) of the mean, median, standard deviation, minimum and maximum. Categorical variables will be summarized by using frequency count and percent distribution.

Principles of statistical analysis

For quantitative efficacy and safety variables, analysis within treatment groups will be presented. Mean changes from baseline and their 95% CIs will be calculated.

For all inferential analyses, p-value will be rounded to three decimal places. Statistical significance will be declared if the rounded p-value will be less than or equal to 0.05.

Subject's accountability

Disposition of patients, patient status and patients excluded from populations will be summarized by treatment group.

Description of the population-description of baseline characteristics

Descriptive statistics will be presented at baseline for demographic and baseline characteristics for the ITT population.

Primary efficacy endpoint

The primary efficacy endpoint (change from baseline in E/Ea ratio) will be analyzed using a linear mixed model for repeated measures including treatment, centre, timepoint, gender, baseline cTnT (normal <URL, abnormal ≥URL), atrial fibrillation (Yes/No) and treatment*timepoint interaction as fixed effects and baseline and baseline*timepoint interaction as covariates.

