# 4.0 STUDY DESIGN

This is a phase II, multicenter, randomized, double-blind, placebo-controlled, parallel group study.

96 Chinese patients and 24 Italian patients will be randomly assigned to one of two doses of istaroxime or placebo in a 2:1 ratio within two sequential cohorts of 60 patients each.

1.0/30/10/2018 Page 9 of 28

This 31-day study includes a screening period (Day -1), a treatment period (Day 1), a post-treatment period (Days 2-4), and a follow-up period (which includes one patient visit on Day 30).

When a patient is considered fully eligible (i.e. s/he fulfills all the inclusion criteria and does not meet any exclusion criteria as stipulated), the patient will be randomized.

Treatment details are presented below:

**Cohort I**: 0.5 µg/kg/min istaroxime or placebo (40 patients randomized to istaroxime 0.5 µg/kg/min group and 20 patients randomized to placebo group).

Istaroxime 0.5  $\mu$ g/kg/min (30  $\mu$ g/kg/h) continuous i.v. infusion for 24 hours not exceeding 72 mg per 24 hours for patients with body weight > 100 kg.

**Cohort II**: 1.0 μg/kg/min istaroxime or placebo (40 patients randomized to istaroxime 1.0 μg/kg/min group and 20 patients randomized to placebo group).

Istaroxime 1.0  $\mu$ g/kg/min (60  $\mu$ g/kg/h) continuous i.v. infusion for 24 hours not exceeding 144 mg per 24 hours for patients with body weight > 100 kg.

A total of 96 Chinese and 24 Italian patients hospitalized with ADHF not requiring inotropic therapy at inclusion into the study (according to the opinion of the Investigator) and not presenting signs and/or symptoms of severe low output state or peripheral hypo perfusion will be randomized.

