# 4.1 SAMPLE SIZE

No formal sample size calculation has been calculated since there is no preliminary study to evaluate these endpoints at 24 hours after the infusion start.

In a previous study (Gheorghiade M. et al. Haemodynamic, echocardiographic, and neurohormonal effects of Istaroxime, a novel intravenous inotropic and lusitropic agent: a randomized controlled trial in patients hospitalized with heart failure. J Am Coll Cardiol. 2008; 51(23): 2276-85), there was a statistically significant decrease of the primary efficacy endpoint with istaroxime 0.5 µg/kg/min respect to placebo at 6 hours (twenty-nine patients in both groups). Since this study will investigate the primary efficacy endpoint at 24 hours and it is supposed that the profile at 24 hours should be similar to the one at 6 hours, it is expected that forty patients per group will be sufficient to evaluate a potential difference between istaroxime groups and placebo group on the primary efficacy endpoint at 24 hours.

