#### 7.7 ANALYSIS OF EFFICACY

# 7.7.1 Primary efficacy endpoint

Analysis will be performed separately for each cohort on ITT and PP populations.

E/Ea ratio will be summarized at each timepoint by treatment group by means of descriptive statistics.

Comparisons between treatment groups will be done using an ANOVA with change from baseline in E/Ea at 24 hours as dependent variable, and treatment as covariate.

The number of patients and the number of patients considered in the model will be provided by treatment. P-values of the fixed effects and covariates will also be presented.

The adjusted means for treatments and 95% CIs will be presented. The difference between the adjusted means for Istaroxime groups versus Placebo will be calculated with the 95% CIs and p-values.

The primary comparison will be Istaroxime 0.5  $\mu$ g/kg/min versus Placebo at 24 hours based on Cohort 1 subjects only. Highest dose of Istaroxime (1.0  $\mu$ g/kg/min) versus Placebo will be tested as a secondary comparison based on Cohort 2 subjects only.

The same analysis will be repeated for change from baseline in E/Ea at 6 hours. All treatment comparisons at 6 hours will be secondary analyses.

E/Ea ratio will also be summarized separated by cohort at each timepoint by treatment group by means of descriptive statistics.

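### Significance is decided on a p-value already rounded to three decimals, so the nominal two-sided level is 0.0505, not the stated 0.05, and the decision can contradict the 95% CI

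*SAP*

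**What the plan says.** Three statements in SAP 7.4 follow one another. The first fixes the level: "Hypothesis testing will be carried out at the alpha = 0.05 level (two-sided) when comparing treatments". The second introduces the rounding: "For all inferential analyses, p-value will be rounded to three decimal places". The third ties the decision to the rounded figure: "Statistical significance will be declared if the rounded p-value will be less than or equal to 0.05".

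Protocol 14.2, under the principles of statistical analysis, has the same rounding to three decimals and the same criterion: "significance will be declared if the rounded p-value will be less than or equal to 0.05".

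For the primary endpoint, SAP 7.7.1 requires an interval beside the p-value: "The difference between the adjusted means for Istaroxime groups versus Placebo will be calculated with the 95% CIs and p-values". The dyspnoea AUC and BNP analyses in SAP 7.7.2 ask for the same pair of results.

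Nothing in either document says that the unrounded p-value governs, or that the interval takes precedence if the two disagree. The decimal-place rules in SAP 9.0 concern listings, derived variables and the display of summary statistics. They do not mention p-values.

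**The concern.** Rounding a p-value for a table is harmless. Here the rounding comes before the decision and is part of it. An unrounded p of 0.0504 becomes 0.050, meets the criterion and is declared significant, although it exceeds the level set two sentences earlier in the same section.

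Two things are at stake. The error rate the SAP states is not the one its decision rule applies. And the 95% interval is built on the unrounded 0.05 level, so the p-value rule and the interval can give opposite answers for the same comparison, including the primary one, with no rule for settling the difference.

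**Working it through.** **Inputs**

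- Stated level: 0.05, two-sided (SAP 7.4).
- Rounding: three decimals, before the decision (SAP 7.4; Protocol 14.2).
- Criterion: rounded p at most 0.05 (SAP 7.4; Protocol 14.2).
- Interval for the treatment difference: 95% (SAP 7.7.1).
- Primary test: ANOVA on the 24-hour change in E/Ea with treatment as the only term, within Cohort I (SAP 7.7.1).
- Group sizes: "40 patients randomized to istaroxime 0.5 µg/kg/min group and 20 patients randomized to placebo group" (SAP 4.0). If all are evaluable, error df = 40 + 20 − 2 = 58.
- SD: none is given in the documents. The level does not depend on it; the worked example below assumes SD = 1.

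**Step 1: the stated level, without rounding.** With 58 df, a two-sided level of 0.05 gives a critical |t| of 2.0017. Comparing the unrounded p with 0.05 gives a level of 0.0500, and the 95% CI uses the same critical value, so test and interval always agree.

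**Step 2: the rule as written.** To three decimals, rounded p ≤ 0.050 is the same event as unrounded p < 0.0505. How exact ties are rounded does not matter, because a continuous p equals 0.0505 with probability zero. Under the null, p is uniform, so

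- level = P(p < 0.0505) = 0.0505
- excess = 0.0505 − 0.0500 = 0.0005
- ratio = 0.0505 / 0.0500 = 1.01, or 1% relative.

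The critical |t| at 58 df falls from 2.0017 to 1.9972 (normal approximation: from 1.9600 to 1.9557).

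**Step 3: simulation.** In 4,000,000 null trials of 40 versus 20 with normal data (Monte Carlo SE about 0.0001):

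| Quantity | Result |
|---|---|
| Rejection rate, unrounded p ≤ 0.05 | 0.0499 |
| Rejection rate, rule as written | 0.0504 |
| Declared significant although unrounded p > 0.05 | 0.0005 |

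The last row is the share of trials in which the rule and the 95% CI disagree: about 1 in 2,000.

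**Step 4: one disagreement in numbers.** Assume SD = 1.

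- SE = √(1/40 + 1/20) = √0.075 = 0.2739
- p = 0.0503 corresponds to t = 1.9990, so difference = 1.9990 × 0.2739 = 0.5475
- 95% CI = 0.5475 ± 2.0017 × 0.2739 = −0.0007 to 1.0956.

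The p-value rounds to 0.050 and is declared significant; the interval includes zero.

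**Step 5: effect on power.** For true differences of 0.5, 0.8 and 1.0 SD, power moves from 0.4348 to 0.4365, from 0.8193 to 0.8204, and from 0.9485 to 0.9490. The gain is below 0.2 percentage points throughout.

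**The case against.** The strongest reply is that this is trivial and transparent. The excess is 0.0005 per test. The rule was fixed in advance, is fully disclosed, appears in both documents and leaves no room for choice after the data are seen. No estimate changes, and no sample size depends on it, since there was no formal calculation. All of that stands, and it is why the point ranks as minor. It does not make the level 0.05: the same section specifies both 0.05 and a rule that yields 0.0505.

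Several narrower points also stand:

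- 0.0505 is a nominal level. It is exact only for a continuous test statistic with its assumptions met. Departures from the assumptions of a treatment-only ANOVA on about 60 patients could move the true level by more than 0.0005 either way.
- The direct conflict is in the SAP. Protocol 14.2 states no separate alpha for treatment comparisons, and its 95% CIs are for means and mean changes within groups. The protocol shares the decision rule but not the contradiction.
- A disagreement might not show in print. A lower limit of −0.0007 would display as zero if E/Ea were recorded to one decimal, which the documents do not say.
- Matching the decision to the interval works for mean differences. The MANOVA tests in SAP 7.7.2 have no corresponding interval.

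None of these removes the mismatch between the stated level and the decision rule.

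**Conclusion.** The point holds, and it is minor. As written, the rule tests at a nominal two-sided level of 0.0505 where the SAP states 0.05. It would declare a treatment difference significant while its 95% CI includes zero whenever the unrounded p lies above 0.05 and below 0.0505. This assumes a continuous test statistic with valid assumptions and ordinary rounding rather than truncation. The figure is per test: it says nothing about multiplicity, and it does not touch the pharmacokinetic linearity criterion in Protocol 14.2, which rests on a 90% CI. Only a result inside that narrow band would be affected, but the documents give no ground for ruling out a borderline primary result.

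**What to change.** In SAP 7.4, replace the decision sentence with one stating that significance is judged by comparing the unrounded two-sided p-value with 0.05, and that rounding to three decimals is for display only. Where an unrounded value near the threshold would print as 0.050, show further decimals so that the printed figure and the conclusion can be reconciled. For the mean differences in SAP 7.7, the decision will then agree with whether the 95% CI excludes zero; for the MANOVA tests the unrounded p-value alone governs.

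The cost is one sentence in the SAP, with no change to design, data or models. Protocol 14.2 should carry the same wording if it is amended for other reasons. An amendment needs ethics committee approval under Protocol 17, so recording the departure in SAP 1.1 is a cheaper alternative.

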3. STUDY DESIGN

This is a phase II, multicenter, randomized, double-blind, placebo-controlled, parallel group study.

96 Chinese patients and 24 Italian patients will be randomly assigned to one of two doses of istaroxime or placebo in a 2:1 ratio within two sequential cohorts of 60 patients each.

This 31-day study includes a screening period (Days -1), a treatment period (Day 1), a post-treatment period (Days 2-4), and a follow-up period (which includes one patient visit on Day 30).

When a patient is considered fully eligible (i.e. s/he fulfills all the inclusion criteria and does not meet any exclusion criteria as stipulated), the patient will be randomized. Treatment details are presented below:

Cohort I: 0.5 µg/kg/min istaroxime or placebo (40 patients randomized to istaroxime 0.5 µg/kg/min group and 20 patients randomized to placebo group).

Istaroxime 0.5 μ g/kg/min (30 μ g/kg/h) continuous i.v. infusion for 24 hours **not exceeding 72** mg per 24 hours for patients with body weight > 100 kg

Cohort II: 1.0 μ g/kg/min istaroxime or placebo (40 patients randomized to istaroxime 1.0 μ g/kg/min group and 20 patients randomized to placebo group).

Istaroxime 1.0 μ g/kg/min (60 μ g/kg/h) continuous i.v. infusion for 24 hours **not exceeding 144** mg per 24 hours for patients with body weight > 100 kg

Escalation to the next dose (second cohort) will occur after completion of the first cohort and determined by the evaluation of the safety data performed by the Data Safety Monitoring Board.

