# 7.7.2 Secondary efficacy endpoints

For echocardiographic parameters, analysis will be performed separately for each cohort on ITT population.

For all other endpoints, analysis will be performed using the combined cohorts on ITT population.

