# 9.0 PROGRAMMING SPECIFICATIONS

The following SAS® code will be used to calculate the age of patient:

age = floor((intck('month', date of birth, date of screening)-(day(date of screening)<day(date of birth)))/12)

The following SAS® code will be used to estimate the MMRM:

```
proc mixed data = dataset;
class tmt timepoint centre gender cTnT atr_fib patient;
model change = tmt timepoint tmt*timepoint centre cTnT atr_fib gender baseline
baseline*timepoint / ddfm=kr;
repeated timepoint / subject=patient type=un;
lsmeans tmt tmt*timepoint / cl;
run;
```

where change represents the change from baseline to post-dose values of the variable, tmt the treatment group, timepoint the timepoint, centre the centre, gender the gender (male/female), cTnT the baseline cTnT (normal <URL, abnormal  $\geq$ URL), atr\_fib the atrial fibrillation (Yes/No), baseline the baseline value of the variable and patient the Patient Number.

The variable tmt will be ordered in SAS® in the following order:

- Istaroxime 0.5 μg/kg/min
- Istaroxime 1.0 µg/kg/min
- Placebo

The following SAS® code will be used to estimate the ANCOVA model:

```
proc mixed data = dataset;
class tmt centre gender cTnT atr_fib;
model variable = tmt centre gender cTnT atr_fib predose;
```

1.0/ 30/10/2018 Page 24 of 28

```
lsmeans tmt / cl; run;
```

where variable represents the efficacy variable (AUC on changes in dyspnoea by VAS score or changes in BNP), tmt the treatment group, centre the centre, gender the gender (male/female), cTnT the baseline cTnT (normal <URL, abnormal ≥URL), atr\_fib the atrial fibrillation (Yes/No), predose the pre-dose of efficacy variable.

The variable tmt will be ordered in SAS® in the following order:

- Istaroxime 0.5 μg/kg/min
- Istaroxime 1.0 μg/kg/min
- Placebo

The following SAS code will be used for the Wilcoxon rank sum test for  $T_{max}$ :

```
proc npar1way wilcoxon hl alpha=0.1 data = dataset; class tmt; var Tmax; run;
```

where tmt represents the treatment groups and Tmax the Tmax parameter value for each patient.

The following SAS code will be used for the ANOVA:

```
proc glm data = dataset;
class tmt;
model variable = tmt;
lsmeans tmt / cl;
run;
```

The following SAS code will be used for the MANOVA:

```
proc glm data = dataset;
class tmt;
model variable = tmt;
contrast 'active vs placebo' group 1 -1;
manova h=tmt;
lsmeans tmt / cl;
run;
```

The global test p-value from Pallai's Trace will be reported.

1.0/30/10/2018 Page 25 of 28

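### Dyspnoea VAS, VAS AUC and BNP compare each dose with placebo pooled over two sequential cohorts, with no cohort term and no by-cohort sensitivity analysis

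*SAP*

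**What the plan says.** Protocol section 3 has patients "randomly assigned to one of two doses of istaroxime or placebo in a 2:1 ratio within two sequential cohorts of 60 patients each". Cohort I is 40 patients on 0.5 µg/kg/min and 20 on placebo; Cohort II is 40 on 1.0 µg/kg/min and 20 on placebo. The cohorts do not overlap in time: "Escalation to the next dose (second cohort) will occur after completion of the first cohort", subject to the safety board's evaluation.

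SAP section 7.4 sets the rule for the comparator: "Statistical analyses will be carried-out pooling together the patients treated with placebo in the two groups with the exception of the echocardiographic parameters". SAP section 7.7.2 repeats it for the secondary endpoints that are not echocardiographic: "For all other endpoints, analysis will be performed using the combined cohorts on ITT population".

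The models are described in SAP sections 7.2 and 7.7.2 and coded in section 9.0. The MMRM code opens with "class tmt timepoint centre gender cTnT atr_fib patient" and the ANCOVA code has "model variable = tmt centre gender cTnT atr_fib predose". Neither contains cohort or calendar time.

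The echo parameters, including the primary E/Ea endpoint, are analysed within cohort (SAP sections 1.1, 7.7.1 and 7.7.2). Placebo is otherwise shown by cohort only for analysis-set counts and baseline demographics (SAP sections 7.5 and 7.6). The protocol's by-cohort sensitivity analysis appears under the primary endpoint (section 14.2). SAP section 7.9 plans no further analysis.

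**The concern.** Each dose exists in one cohort only, so its randomised comparator is the 20 placebo patients of that cohort. The other 20 in the pooled group were enrolled in a different period and could not have received that dose. The pooled contrast is therefore half concurrent and half historical.

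If the response level differs between the two periods, for example through background care or case mix that the covariates do not capture, the difference enters the treatment estimate. It enters with opposite signs for the two doses, so it can imitate or hide a dose response in a study that compares two doses. Nothing planned for the non-echo endpoints would reveal this, because neither a model term nor an outcome table separates the cohorts.

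**Working it through.** **Inputs.** From Protocol section 3 and SAP section 4.0: 40 active and 20 placebo per cohort. From SAP section 7.4: two-sided alpha 0.05. The documents give no SD and no drift size, so results are in SD units and d is assumed.

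**The plan's own figure.** SAP section 4.1 relies on forty patients per group without a formal calculation. Placebo reaches 40 only by pooling: 20 + 20 = 40. The total agrees: 2 × (40 + 20) = 120 = 96 + 24.

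**Bias without adjustment.** Let Cohort II differ from Cohort I by d in every arm, with no drug effect. The pooled placebo mean shifts by d × 20/40 = d/2.
- 0.5 µg/kg/min minus pooled placebo: 0 − d/2 = −d/2.
- 1.0 µg/kg/min minus pooled placebo: d − d/2 = +d/2.
- Apparent difference between the doses: d/2 − (−d/2) = d.

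An uneven split changes the shares. With 16 and 24 placebo patients, the biases are −0.60d and +0.40d.

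**Bias with centre in the model.** Suppose allocation is 2:1 in every centre and cohort, and the cohorts are equal in size. Let p be the share of a centre's patients who are in Cohort II, and Q the patient-weighted mean of p(1 − p). The least-squares equations then give biases of −bd and +bd, with b = 6Q/(1 + 8Q). The documents do not say how centres overlap, so these splits are assumptions:
- Every centre recruits equally to both cohorts: Q = 0.25, b = 1.5/3 = 0.50.
- All 24 Italian patients in Cohort I, and the other 96 at p = 60/96 = 0.625: Q = 0.8 × 0.2344 = 0.1875, b = 1.125/2.5 = 0.45.
- Half of each cohort from centres active in that cohort only: Q = 0.125, b = 0.75/2 = 0.375.
- Every centre active in one cohort only: Q = 0, b = 0.

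**Type I error, unadjusted.** SE = √(1/40 + 1/40) = 0.224 SD. With s = (d/2)/0.224, the error is 1 − Φ(1.96 − s) + Φ(−1.96 − s).

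| Assumed d (SD) | Bias per dose (SD) | Two-sided type I error |
|---|---|---|
| 0.2 | 0.10 | 7.3% |
| 0.3 | 0.15 | 10.3% |
| 0.5 | 0.25 | 20.1% |

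A noncentral t with 117 df, with the residual SD inflated for drift within placebo, gives 7.2%, 10.1% and 19.3%.

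**With a cohort term.** Intercept, cohort and two dose effects fit the four cohort-by-arm cells exactly, so each dose is compared with its own cohort's placebo and the drift bias is 0.
- SE = √(1/40 + 1/20) = 0.274 SD; 0.274/0.224 = 1.22.
- Difference detectable with 80% power: (1.960 + 0.842) × 0.224 = 0.63 SD pooled; 2.802 × 0.274 = 0.77 SD within cohort.
- Power at 0.63 SD: about 80% pooled; Φ(0.6265/0.2739 − 1.960) = Φ(0.33), about 63%, within cohort.

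**The case against.** A reader might infer that half of any drift becomes treatment effect on every non-echo endpoint. The documents do not support that, for these reasons:
- The MMRM and ANCOVA adjust for centre, sex, cTnT class, atrial fibrillation and the baseline value. Only drift that these leave unabsorbed is at issue, and d/2 is the largest of the centre scenarios at the planned split.
- A shift in country mix is contained in an additive centre effect. An additive assay shift cancels from BNP change scores, and VAS has no assay. Residual case mix and background care remain.
- Only three endpoints are tested. Readmission, worsening heart failure, length of stay and safety are summarised without p-values.

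It is also tempting to say that the SAP contradicts itself by splitting echo alone. SAP section 1.1 places the reason in a memo to file that is not among the documents, so whether that reason extends to VAS or BNP cannot be judged.

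Finally, pooling can be defended as a trade of possible bias for precision on secondary endpoints in a phase II trial, and the demographic tables by cohort would show some change in case mix. Both points are fair. They support keeping the pooled analysis in some role. They do not support leaving the randomised comparison out altogether: centre removes none of the drift when every centre recruits equally to both cohorts, and demographic tables do not show drift in outcome.

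**Conclusion.** The point holds for dyspnoea VAS, VAS AUC and BNP. Each dose was randomised only against its own cohort's placebo, and the planned tests use a comparator that is half non-concurrent, with no cohort term and no check. At the planned 20/20 split the bias is up to d/2 per dose in opposite directions, and up to d in the apparent difference between doses, where d is the drift before covariate adjustment.

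The type I error of about 7% to 20% rests on an assumed d of 0.2 to 0.5 SD and an unadjusted comparison. It is an upper case for the adjusted models when d is measured in their residual SD. It illustrates sensitivity and does not predict the error rate of this trial.

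In the unadjusted descriptive tables the displayed mean contrast is distorted by d/2, but no p-value is affected. The primary and other echo endpoints are analysed within cohort, the interim cTnT review has only concurrent placebo, and PK has no placebo contrast, so none of these is affected.

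**What to change.** In SAP sections 7.2, 7.7.2 and 9.0, add cohort as a fixed effect to the VAS MMRM and to the VAS AUC and BNP ANCOVAs. Add cohort by timepoint in the MMRM, because drift need not be constant over the 48 hours. Keep the pooled model as a sensitivity analysis. At minimum, keep the pooled model as the main analysis and plan the within-cohort comparison as a sensitivity analysis for all three endpoints.

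In SAP section 7.4, and in the safety and descriptive efficacy tables, show placebo by cohort as well as pooled, as sections 7.5 and 7.6 already do for counts and demographics.

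No new data are needed. The cost is precision: the comparison becomes 40 versus 20, with the 22% larger standard error and the loss of power from about 80% to 63% at 0.63 SD shown above. The SAP already accepts 40 versus 20 for E/Ea.
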